4.2.2. Adherence to GS-5829

The total amount of doses administered in mg will be summarized using descriptive statistics.

The presumed total amount of doses administered to a subject will be determined by the data collected on the drug accountability CRF using the following formula:

Total Amount of Doses Administered

$$(\Sigma \text{Amount. of Doses Dispensed in mg}) - (\Sigma \text{Amount. of Doses Returned in mg})$$

4.2.2.1. On-Treatment Adherence

The level of on-treatment adherence to GS-5829 will be determined by the total amount of study drug administered relative to the total amount of GS-5829 expected to be administered during a subject's actual on-treatment period. Investigator-prescribed interruption and reductions as specified in the protocol will be taken into account.

The level of on-treatment adherence will be expressed as a percentage using the following formula:

$$\text{On-Treatment Adherence (\%)} = \left(\frac{\text{Total Amount of Study Drug Administered}}{\text{Study Drug Expected to be Administered on Treatment}} \right) \times 100$$

If there are treatment periods that bottles are not returned, or the return information is missing, these periods will be excluded from the on-treatment adherence calculation for both total amount of study drug administered, and study drug expected to be administered. If subjects never returned any bottle, the adherence will be set as missing.

Descriptive statistics for the level of on-treatment adherence with the number and percentage of subjects belonging to adherence categories ($< 75\%$, $\geq 75\%$) will be provided by treatment group for the Safety Analysis Set.

A by-subject listing of study drug administration and drug accountability will be provided separately for GS-5829 by subject ID number (in ascending order) and visit (in chronological order). Separate listing of enzalutamide administration will also be provided.

4.3. Protocol Deviations

Subjects who did not meet the eligibility criteria for study entry but enrolled in the study will be summarized regardless of whether they were exempted by the sponsor or not. The summary will present the number and percentage of subjects who did not meet at least 1 eligibility criterion and the number of subjects who did not meet specific criteria by treatment group based on the All Enrolled Analysis Set. A by-subject listing will be provided for those subjects who did not meet at least 1 eligibility (inclusion or exclusion) criterion. The listing will present the eligibility criterion (or criteria if more than 1 deviation) that subjects did not meet and related comments, if collected.

Protocol deviations occurring after subjects entered the study are documented during routine monitoring. The number and percentage of subjects with important protocol deviations by deviation reason (eg, nonadherence to study drug, violation of select inclusion/exclusion criteria) will be summarized by treatment group for the All Enrolled Analysis Set. A by-subject listing will be provided for those subjects with any important protocol deviation.

5. BASELINE CHARACTERISTICS

5.1. Demographics and Baseline Characteristics

Subject demographic variables (ie, age, sex, race, and ethnicity) and baseline characteristics (body weight [in kg], height [in cm], body mass index [BMI; in kg/m²]) will be summarized by treatment group and overall using descriptive statistics for continuous variables and using number and percentage of subjects for categorical variables. The summary of demographic data will be provided for the All Enrolled Analysis Set.

A by-subject demographic listing, including the informed consent date, will be provided by subject ID number in ascending order.

5.2. Other Baseline Characteristics

Not applicable.

5.3. Medical History

Medical history will be collected at screening for disease-specific and general conditions (ie, conditions not specific to the disease being studied).

General medical history data will not be coded but will be listed only. A by-subject listing of general medical history will be provided by subject ID number in ascending order.

5.4. Prior Anticancer Therapy

Number of prior regimens, time since the completion of last regimen, and specific prior treatment (enzalutamide, abiraterone, and chemotherapy) will be summarized by treatment group using descriptive statistics based on the Full Analysis Set. A partial completion date will be imputed using the algorithm defined below.

All partial dates of the completion of last regimen will be identified, and the partial dates will be imputed as follows:

- If day and month are missing but year is available, then the imputed day and month will be 01 Jan.
- If day is missing but the month and year are available, then the imputed day will be the first day of the month.
- Partial date will not be imputed if the year is missing.

A by-subject listing will be provided for prior anticancer therapies, on-study anticancer therapies, prior and on-study radiation therapy, and prior and on-study surgery and procedures each by subject ID number in ascending order.

6. EFFICACY ANALYSES

6.1. Primary Efficacy Endpoint

6.1.1. Definition of the Primary Efficacy Endpoint

The primary efficacy endpoint of this study is non-progression rate at Week 24 defined as the proportion of subjects who don't progress by Week 24. The progression is determined by the investigators based on Prostate Cancer Working Group 2 (PCWG2) Criteria for lesion scans, bone scans and PSA assessments together. Subjects will be considered as having definitive disease progression if any of three progression criteria meets. Progression-free survival (PFS), defined as the interval from start of study drug to the earlier of the first documentation of definitive disease progression or death from any cause. Definitive disease progression is determined by investigator based on PCWG2 criteria.

The date of definitive progression will be the time point at which progression is first identified. The death from any cause to be considered as PFS event should occur within the time window of 2 consecutive scheduled tumor assessments after the last tumor assessment. Non-evaluable (NE) and no disease (ND) are considered as not adequate.

Subjects will be censored on the date of Study Day 1 if

- no adequate baseline target lesion assessment nor bone scan is available (note: baseline PSA assessment missing is allowed) and subject didn't die before or on the 2nd scheduled post-baseline tumor assessment without receiving anti-cancer therapy;
- or if no adequate post-baseline tumor assessment is available and subjects didn't die
- or if no adequate post-baseline tumor assessment is available and subjects died after the 2nd scheduled tumor assessment.

Subjects will be censored on the date of last adequate post-baseline tumor assessment, or Day 1 if the last post-baseline adequate tumor assessment doesn't exist, for the following situations:

- who do not have documented progression or die, or
- who start new anticancer therapy before documented progression, or
- who start new anticancer therapy before death without documented progression, or
- who have ≥ 2 consecutive missing post-baseline tumor assessments immediately before documented progression, or
- who have ≥ 2 consecutive missing post-baseline tumor assessments immediately before death without documented progression

Table 6-1 below provides detailed event/censoring scheme for PFS derivation and the derivation diagram provides all decisions on event/censoring indicators and time.

Table 6-1. Event/Censoring Scheme of Analysis for PFS

PFS Derivation Step	Situation	Date of Progression or Censoring	Outcome
1	No adequate baseline tumor assessments and subjects didn't die before or on the 2nd scheduled post-baseline tumor assessment	Study Day 1	Censored
1	No adequate baseline tumor assessments and subjects died before or on the 2nd scheduled post-baseline tumor assessment without receiving anti-cancer therapy	Date of death	Event
1	No adequate baseline tumor assessments, subjects died before or on the 2nd scheduled post-baseline tumor assessment and received anti-cancer therapy	Study Day 1	Censored
2	No adequate post-baseline tumor assessments and subjects did not die	Study Day 1	Censored
2	No adequate post-baseline tumor assessments and subjects died after the 2nd scheduled post-baseline tumor assessment	Study Day 1	Censored
2	No adequate post-baseline tumor assessments and subjects died before or on the 2nd scheduled post-baseline tumor assessment without receiving anti-cancer therapy	Date of death	Event
2	No adequate post-baseline tumor assessments, subjects died before the 2nd scheduled post-baseline tumor assessment and received anti-cancer therapy	Study Day 1	Censored
3	Documented progression and didn't receive anti-cancer therapy or have ≥ 2 consecutive missing post-baseline tumor assessments immediately before documented progression	Date of the first documented progression	Event
3	Death without progression and within the time window of 2 consecutive scheduled post-baseline tumor assessments after the last tumor assessment and didn't receive anti-cancer therapy or have ≥ 2	Date of death	Event

PFS Derivation Step	Situation	Date of Progression or Censoring	Outcome
	consecutive missing post-baseline tumor assessments immediately before death		
3	No documented progression or death and didn't receive anti-cancer therapy or have ≥ 2 consecutive missing post-baseline tumor assessments	Date of the last adequate post-baseline tumor assessment	Censored
4	Start new anticancer therapy without or before documented progression or death or have ≥ 2 consecutive missing post-baseline tumor assessments immediately before documented progression or death	The later one of 1) Date of the last adequate post-baseline tumor assessment on/prior to the new anticancer therapy start date and/or the consecutive missing 2) Study Day 1	Censored

When the date of initiation of anticancer therapy other than the study treatment is incomplete or missing, the following algorithm will be followed:

- If the day is missing but the month and year are available, then the imputed day will be the first day of the month.
- If day and month are missing but year is available, then the imputed day and month will be 01Jan or the last day of the month for the last adequate disease assessment if they have the same year, whichever is later.

Every attempt will be made to ensure that complete death dates are recorded. In those rare instances where complete death dates are not recorded, the following algorithm will be used:

- If day is missing but the month and year are available, then the imputed date will be the 1st day of the month or the last known alive date + 1, whichever is later.
- If day and month are missing but year is available, then the imputed date will be 01Jan of that year or the last known alive date + 1, whichever is later.

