### 3.3. Study Treatments

Subjects who meet eligibility criteria will receive GS-5829 as a single agent or combined with enzalutamide orally once daily. Each cycle will consist of 28 days. Safety and efficacy assessments will occur on an outpatient basis including assessment of tumor response, physical exam, vitals, electrocardiogram (ECG), collection of blood samples (for routine safety labs, GS-5829 PK, PD markers, and biomarkers at applicable visits), and assessment of AEs. In addition, subjects will undergo a bone scan and CT (or MRI) every 12 weeks.

A subject who does not show evidence of disease progression may continue receiving GS-5829 as a single agent or combined with enzalutamide once daily until disease progression (clinical or radiographic), unacceptable toxicity, withdrawal of consent, or other reasons specified in Section 3.4. Subjects who have progressive disease by PSA measurements alone may continue study drug.

Following treatment, subjects will be followed for safety for 30 days and for survival.

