### 4.2. Inclusion Criteria

Subjects must meet all of the following inclusion criteria to be eligible for participation in this study.

- 1) Male  $\geq$ 18 years of age
- 2) Histologically or cytologically confirmed prostate cancer (subjects with primary neuroendocrine carcinoma of prostate are excluded)
  - Phase 1b Monotherapy Escalation: Subjects must have documented progressive disease by meeting at least one of the PCWG2 criteria ([Appendix 4](#)) despite treatment with abiraterone and/or enzalutamide
  - Phase 1b Combination Therapy Dose Escalation **and** Phase 2 Combination Dose Expansion (Group 2): Subjects must have documented progressive disease by meeting at least one of the PCWG2 criteria, despite treatment with abiraterone. They may **not** have received prior enzalutamide or chemotherapy for mCRPC
  - Phase 2 Monotherapy Dose Expansion (Group 1): Subjects must have documented progressive disease by meeting at least one of the PCWG2 criteria, despite treatment with enzalutamide. They may have received prior abiraterone, but not prior chemotherapy, for mCRPC
  - Phase 2 Combination Therapy Dose Expansion (Group 3): Subjects must have documented progressive disease by meeting the PCWG2 criteria for PSA progression, but not radiographic progression, despite treatment with enzalutamide. They may have received prior abiraterone, but not prior chemotherapy, for mCRPC (similar to Group 1); however, they must also have been on continuous enzalutamide therapy for at least 12 weeks days prior to Cycle 1, Day 1.
- 3) Castration-resistant disease defined as ongoing androgen deprivation therapy with GnRH analogue or bilateral orchiectomy and serum testosterone level  $\leq$  1.73 nmol/L (50 ng/dL) at screening visit. Subjects who have not had a bilateral orchiectomy must have a plan to maintain effective GnRH-analogue therapy for the duration of the trial.

- 4) Metastatic disease documented by bone lesions on bone scan or by measurable soft tissue disease by CT/MRI. Patients whose disease spread is limited to regional pelvic lymph nodes are not eligible
- 5) All acute toxic effects of any prior antitumor therapy resolved to Grade  $\leq 1$  before the start of study drug dosing (with the exception of alopecia [Grade 1 or 2 permitted] and neurotoxicity [Grade 1 or 2 permitted])
- 6) Eastern Cooperative Oncology Group (ECOG) Performance Status of  $\leq 1$
- 7) Life expectancy of  $\geq 3$  months, in the opinion of the Investigator

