## **6.10.          Post Study Care**

If a subject has discontinued the study treatment due to toxicity, he/she should not have withdrawal of consent recorded as the reason for discontinuation. Instead, the reason for discontinuation must be recorded as due to adverse event.

Every attempt should be made to keep the subject in the study and continue collecting CT or MRI scans for tumor assessment at every 12 weeks until disease progression or initiation of systemic anti-tumor therapy other than treatment per protocol. If this is not possible or acceptable to the subject or investigator, the subject may be withdrawn from the study. The subject will be asked to attend the post-treatment follow-up assessment visit above when discontinuing from the study treatment.

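### SAP Table 6-1 lets a documented PSA progression be censored at Study Day 1 when no post-baseline scan is adequate, and the SAP does not say how CT/MRI and bone scan combine after baseline.

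*SAP*

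**What the plan says.** SAP 6.1.1 counts progression when any one of three PCWG2 criteria is met: lesion scan, bone scan or PSA. On scan adequacy it says "Non-evaluable (NE) and no disease (ND) are considered as not adequate". It does not define ND, and the lesion-scan response categories in SAP 6.2.1 do not list it.

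The rules for censoring at Study Day 1 are worded differently before and after baseline:

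- Baseline bullet: "no adequate baseline target lesion assessment nor bone scan is available", with a note that a missing baseline PSA is acceptable.
- Post-baseline bullet: "or if no adequate post-baseline tumor assessment is available and subjects didn't die". No modality is named.
- Table 6-1, step 2: "No adequate post-baseline tumor assessments and subjects did not die", with outcome censored at Study Day 1.

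Step 3 of the same table makes documented progression an event on the date it was first documented, unless other anticancer therapy or at least two consecutive missing assessments came first. SAP 6.1.2 takes the Week-24 non-progression rate from the Kaplan-Meier PFS analysis and adds a simple count.

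On disease sites, Protocol 4.2 criterion 4 requires "Metastatic disease documented by bone lesions on bone scan or by measurable soft tissue disease by CT/MRI", so disease at one site only is allowed. Protocol 3.3 states that "subjects will undergo a bone scan and CT (or MRI) every 12 weeks".

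**The concern.** A subject with disease in bone only is expected to have CT/MRI scans that show no disease, and a subject with soft-tissue disease only is expected to have bone scans that show none. These are completed negative scans, yet they are coded with the unevaluable ones. That raises the question of who ends up without an adequate post-baseline assessment, and what happens to that subject's events.

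The steps of Table 6-1 are numbered, and step 2 comes before step 3. If a program applies them in that order, a subject with no adequate post-baseline scan leaves at step 2 before anyone asks whether he progressed. PSA is drawn on Day 1 of every cycle, independently of imaging, so PSA progression can be on record without an adequate scan. Censoring such a subject at Day 1 removes a known failure, and the reason for removal is not independent of outcome. The Week-24 rate can then only stay the same or rise.

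**Working it through.** The plan gives no figure for this point. The check is a reading of the rules, followed by simple arithmetic on size.

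**Step 1. What makes an assessment adequate?** The baseline bullet requires both the lesion assessment and the bone scan to be inadequate before a subject is censored. Table 6-1 step 1 restates that condition using the general term tumor assessments. In this table, therefore, the term covers either modality. Step 2 uses the same term. Criterion 4 ensures that every eligible subject has disease in at least one modality, so an evaluable scan of that site gives an adequate assessment. An ND reading at the other site removes nobody.

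**Step 2. Who is left without an adequate assessment?** Only subjects whose diseased site was missed or NE at every post-baseline opportunity, with any other scan ND, NE or missed.

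**Step 3. Which progressions can occur in such subjects?** A lesion or bone progression normally rests on an evaluable scan, so step 2 does not apply. PSA progression needs no scan, so it is the exposed criterion.

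**Step 4. A constructed case that the protocol allows.** Monotherapy, bone-only disease, PSA falling through Week 8.

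| Time | Finding |
|---|---|
| Week 12 | CT reads ND; bone scan NE; PSA meets the progression threshold |
| Week 16 | PSA rise confirmed (4 weeks later; Appendix 5 asks for 3 or more); treatment stops |
| End of treatment | No new scans required, since the last were within 4 weeks (Protocol 6.5.5) |

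He is alive and has started no new therapy, and only one scheduled assessment is inadequate. Under step 2 he is censored at Study Day 1. Under step 3 he is an event at Week 12. Both rows fit, and the visible text states no precedence.

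The conflict has a limit. If two or more consecutive assessments were missing just before progression, step 3 no longer applies, and step 4 censors the subject by design.

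**Step 5. Size.** A subject censored at Day 1 contributes nothing to the later risk sets. Take a group of n with k subjects event-free at Week 24 and no other censoring (assumption):

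- Progression counted: rate = k/n.
- Progressor censored at Day 1: rate = k/(n − 1).
- Rise = k/(n − 1) − k/n = k/[n(n − 1)], which is largest at k = n − 1, where it equals 1/n.

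The planned cohorts are 3 to 6 subjects (SAP 1.2). The values of k are illustrative.

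| n | k | Counted | Censored at Day 1 | Rise (points) |
|---|---|---|---|---|
| 6 | 1 | 16.7% | 20.0% | 3.3 |
| 6 | 3 | 50.0% | 60.0% | 10.0 |
| 6 | 5 | 83.3% | 100% | 16.7 |
| 3 | 1 | 33.3% | 50.0% | 16.7 |
| 3 | 2 | 66.7% | 100% | 33.3 |

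With k = 0 the rate is zero either way. If cohorts are pooled, n grows and the effect of one subject shrinks.

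**The case against.** The best defence is that the SAP points to a derivation diagram said to settle every event and censoring decision. It is not visible in the available text, and its absence there is no fault of the plan. It may already put documented progression first. That stands, and is why checking it is part of the fix.

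One could also say that a PSA value is itself a tumor assessment, so a PSA progressor never reaches step 2. The text points the other way: the baseline adequacy rule names only the two imaging modalities and sets PSA aside.

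Third, results are descriptive, Phase 2 was not opened (SAP Introduction), and the Week-24 count is reported beside the Kaplan-Meier rate. This limits the consequences. However, the SAP does not say how the count treats a subject censored at Day 1.

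A reader might infer something stronger: that all bone-only subjects are censored at Day 1 because tumor assessment means CT/MRI, as in Protocol 6.10 ("continue collecting CT or MRI scans for tumor assessment at every 12 weeks"). The documents do not support this. Section 6.10 describes scan collection after treatment stops and defines no SAP term, while the SAP's own baseline bullet and step 1 treat the term as covering either modality. Soft-tissue-only subjects would keep adequate CT scans on either reading.

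Nor does the SAP say that a performed scan read as ND counts as missing for the two-consecutive-missing rule.

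**Conclusion.** The point holds in a limited form. Two rows of Table 6-1 can apply to the same living subject with opposite outcomes, and the step 2 outcome contradicts the rule that any one criterion is definitive progression. The related gap is that adequacy is set by response code, without defining ND or saying how modalities combine after baseline. That gap needs clarifying but does not by itself censor single-site subjects.

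The documents do not give the number affected. It is probably small, because both scans are scheduled every 12 weeks and at end of treatment, and all of them must fail to give an adequate assessment. The figures above rest on one affected subject, cohorts of 3 to 6 and no other early censoring. They apply to the Phase 1b cohorts only. The share of bone-only subjects is not given, so no claim about lost sample size, or about a rate dominated by soft-tissue disease, can be made. Severity is minor to moderate.

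**What to change.** 1. In SAP 6.1.1 and Table 6-1, state that documented progression on any criterion (lesion, bone or PSA) is handled at step 3 and is never overridden by step 2. Leave the rules on new anticancer therapy and on two or more consecutive missing assessments unchanged.
2. State that after baseline, as at baseline, an evaluable scan in a modality that showed disease at baseline makes the assessment adequate. Define ND, and say that ND in a modality negative at baseline is an evaluable non-progression result that does not void the time point. A visit at which no diseased site was evaluably imaged stays inadequate; item 1 is what protects a PSA event there.
3. Check that the derivation diagram agrees with both statements.

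The cost is SAP wording and a change to the PFS program. No new data are needed.

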#### **6.5.5. End of Treatment (EOT) Visit**

The following procedures will be conducted when a subject discontinues GS-5829, with a window of  $\pm$  7 days, and prior to initiating a new anti-cancer regimen:

- Complete Physical examination, including weight
- Vital signs (pre-dose only)
- Triplicate 12-lead ECG
- ECOG performance status
- Laboratory assessments and blood sampling
  - Chemistry
  - CBC with differential
  - Coagulation
  - Urinalysis
  - PSA
- **cci** [REDACTED]
- Bone scan (not necessary if restaging scan was performed within the prior 4 weeks)
- CT with contrast or MRI (not necessary if restaging scan was performed within the prior 4 weeks)
- Record any adverse events
- Concomitant medications review
- IP/Dosing Diary accountability

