7.1.5.2. Incomplete Dates

If the onset date of the AE is incomplete and the AE stop date is not prior to the first dosing date of study drug, then the month and year (or year alone if month is not recorded) of onset determine whether an AE is treatment emergent. The event is considered treatment emergent if both of the following 2 criteria are met:

- The AE onset is the same as or after the month and year (or year) of the first dosing date of study drug, and
- The AE onset date is the same as or before the month and year (or year) of the date corresponding to 30 days after the date of the last dose of study drug

An AE with completely missing onset and stop dates, or with the onset date missing and a stop date later than the first dosing date of study drug, will be considered to be treatment emergent. In addition, an AE with the onset date missing and incomplete stop date with the same or later month and year (or year alone if month is not recorded) as the first dosing date of study drug will be considered treatment emergent.

In case when the AE onset date is incomplete and needs to be imputed, the following algorithm will be followed:

- If the day is missing but the month and year are available, then the imputed day will be the first day of the month or the first dosing date if they have the same month and year, whichever is later.
- If the day and month are missing but year is available, then the imputed day and month will be 01Jan or the first dosing date if they have the same year, whichever is later.

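### A new-therapy start with the day missing is set to the 1st of the month with no floor, so it can pre-date, and censor, a progression documented later that month

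*SAP*

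**What the plan says.** SAP 6.1.1 censors PFS for subjects "who start new anticancer therapy before documented progression". Table 6-1 step 4 repeats the trigger ("Start new anticancer therapy without or before documented progression or death") and sets the censoring date to the later of Study Day 1 and the "Date of the last adequate post-baseline tumor assessment on/prior to the new anticancer therapy start date".

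Two bullets below the table cover incomplete therapy dates:

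- Day missing: "If the day is missing but the month and year are available, then the imputed day will be the first day of the month". There is no lower limit.
- Day and month missing: "01Jan or the last day of the month for the last adequate disease assessment if they have the same year, whichever is later". This is a lower limit tied to the last disease assessment.

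Other on-study date rules in the SAP also have a floor. For a death with the day missing, "the imputed date will be the 1st day of the month or the last known alive date + 1, whichever is later". For an adverse event onset (SAP 7.1.5.2), "the imputed day will be the first day of the month or the first dosing date if they have the same month and year" applies, whichever is later.

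No exception in SAP 6.1.1 covers a progression documented in the same month as a partial therapy date. SAP 6.1.2 takes the Week 24 non-progression rate from the Kaplan-Meier PFS analysis and also reports a simple count of subjects without progressive disease at Week 24.

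**The concern.** Therapy given because of a progression can cancel that progression in the analysis. If a scan shows progression on 10 March and the next treatment is recorded only as March, the imputed start is 1 March. The derivation then treats the therapy as coming first, drops the progression and censors the subject. If no adequate post-baseline assessment precedes 1 March, the subject is censored at Study Day 1 and contributes no follow-up.

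The two bullets also give results in the wrong order of quality. A record showing only the year keeps the event, while the fuller record showing month and year can lose it. At stake are the Kaplan-Meier PFS curve and the Week 24 rate, in cohorts small enough for one event to show.

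**Working it through.** **The plan's own figure.** The documents give no number for this imputation rule. The one figure stated for the endpoint (SAP 1.3) is that more than 10 of 20 subjects without progression puts the 90% lower bound above 30%. The exact two-sided bound for 11/20 is 34.7%, so the statement reproduces. It is not in dispute here.

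**Inputs from the documents.** Censoring trigger and date: SAP 6.1.1 and Table 6-1 step 4. Scans every 12 weeks: Protocol 6.2.9.2. Kaplan-Meier by treatment group: SAP 6.1.2. Cohorts of 3 to 6: SAP 1.2. Confirmation rules: Protocol Appendix 5.

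**Assumed.** Calendar dates, the lag from progression to new therapy, and the event patterns.

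**Step 1: one subject through the rules.** First dose 4 January 2017; Week 12 scan 84 days later, 29 March, showing progression; new therapy truly started 31 March.

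| Recorded start | Imputed start | Against 29 March | PFS result |
|---|---|---|---|
| 31 March 2017 | none needed | after | event, 29 March |
| March 2017 | 1 March | before | censored, Study Day 1 |
| 2017 | 31 March (later of 1 January and the end of the assessment month) | after | event, 29 March |

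**Step 2: how often the order reverses, given a missing day.** In a 30-day month, let progression fall on day d, uniformly, and therapy start L days later. The event is lost when d is at least 2 (a start on the same day is not before) and d + L is at most 30. The share is (30 - L - 1)/30. The last column applies the rule to every progression date from 2016 to 2019.

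| Lag L | Formula | Real calendar |
|---|---|---|
| 7 days | 22/30 = 73% | 74% |
| 14 days | 15/30 = 50% | 51% |
| 21 days | 8/30 = 27% | 28% |
| 28 days | 1/30 = 3% | 5% |
| 42 days or more | 0 | 0 (no month is that long) |

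These shares are conditional on the day being missing.

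**Step 3: effect on the Week 24 Kaplan-Meier estimate.**

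- Cohort of 6, three Week 12 progressions, no other event: 3/6 = 50%. With one recoded to Study Day 1, 5 are at risk with 2 events: 3/5 = 60%. Censoring at any other time before Week 12 gives the same 60%.
- Cohort of 6, two progressions at Week 12 and one at Week 24: (4/6)(3/4) = 50%. Losing a Week 12 event gives (4/5)(3/4) = 60%. Losing the Week 24 event, censored at the Week 12 scan, gives 4/6 = 66.7%.
- Group of 20, five progressions at each of Weeks 12 and 24: (15/20)(10/15) = 50%. Losing one Week 12 event gives (15/19)(10/15) = 52.6%.

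**Step 4: direction.** Kaplan-Meier passes a censored subject's weight to those still under observation. Recoding an event to an earlier censoring therefore gives every later subject at least as much weight as before. From the date of the lost progression onward the curve can only rise or stay level. Before that date it can dip slightly if other events fall in the gap, because the risk set is smaller. A progression documented by Week 24 thus affects the Week 24 rate in one direction only.

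**The case against.** The case against is mainly about reach, and much of it stands.

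- **Confirmation lengthens the lag.** Under Protocol Appendix 5, bone progression at the first reassessment needs a further scan at least 6 weeks later but is dated to the first scan. If new therapy waits for confirmation, the lag is at least 42 days and reversal is impossible. PSA progression after a decline needs a second value at least 3 weeks later, where the share is already down to 27-28%. Short lags fit mainly soft-tissue progression, unconfirmed progression, and PSA progression without prior decline.
- **PSA-only progressors may stay on study drug** (Protocol 3.3). Their progression date can precede new therapy by months.
- **Phase 1b collects little later therapy.** The 30-day visit is the final one, and post-study therapy is specifically sought there from subjects who stopped for reasons other than progression (Protocol 6.6). Follow-up for later therapy is Phase 2 only (Protocol 6.7). The remaining route is mainly the concomitant medication review.
- **Little rests on the result.** Phase 1b efficacy is secondary, no formal testing is done (SAP 3.5), and the study was discontinued before Phase 2 (SAP 1).

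These points shrink the exposed set without emptying it, and none explains why this bullet lacks the floor its neighbour has.

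A reader might infer three stronger claims that the documents do not support. First, that a missing day is the usual kind of incomplete date, or that 27% to 73% of progressions are lost: no frequency of missing days is given. Second, that the protocol guarantees progression before therapy: Protocol 6.5.5 places end-of-treatment procedures "prior to initiating a new anti-cancer regimen", which orders that visit and the therapy only. Third, that every reported efficacy result is inflated: the by-count Week 24 figure need not change.

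**Conclusion.** The concern holds in a limited form. The missing-day rule, read with Table 6-1 step 4, can turn a true progression event into a censored observation when therapy truly followed progression in the same calendar month and progression was not on the 1st. If therapy truly came first, censoring is what the SAP intends.

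The total effect cannot be computed, because neither the frequency of missing days nor the lag to new therapy is given. Per affected record it can be visible: 10 to 17 percentage points in the illustrative cohorts of 6, against under 3 points in a group of 20, a size that never enrolled. Those figures rest on assumed event patterns. The Kaplan-Meier rate could also differ from the by-count rate with no specified analysis to explain why. This should be corrected, but it does not undermine the analysis as a whole.

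**What to change.** Give the missing-day bullet in SAP 6.1.1 the same floor as the year-only bullet. If the last adequate disease assessment, including one that documents progression, falls in the same month and year as the partial therapy date, impute the last day of that month; otherwise impute the 1st. This keeps the imputed date inside the recorded month. Imputing the day after the assessment would not: an assessment on 31 March would give 1 April.

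The cost is one sentence in the SAP and one line in the PFS program, with no new data. SAP 1 provides for finalization before the database is finalized and for later changes to be documented in the study report.

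The floor has its own error. Therapy that truly began on 3 March, before a progression on 10 March, would be counted as an event that the SAP means to censor, making the reported rate slightly less favourable. An end-of-month date can also fall after a death earlier that month, as it already can under the year-only bullet, so the program should flag such records. Listing every subject whose partial therapy date shares a month with a progression would show how many results depend on the choice.
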